4.4.8. Treatment Compliance

Participants are instructed to record the date and timing of all doses on a memory aid. Participants are asked to bring the vial of medication and memory aid to the study personnel at their follow-up visit. Study personnel reviews adherence to the study medication schedule with the participants, including the participant's memory aid, and record this on the appropriate data collection form at Visit 2 (TOC). See Section 3.3.5 for the definition of adherence to treatment.

4.5. Efficacy and Safety Variables

For safety and efficacy analyses, multiple observations within a specific visit period are accepted. In the case of multiple observations within a specific window, the assessment value that is closest to the scheduled visit window will be used in the analyses for the post-baseline records. For screening and baseline visits, the last assessment value will be used. All the recorded data will be listed. If observations have the same distance to the scheduled assessment, the latest one will be used.

Efficacy Variables

See Section 3.3 for efficacy variable definitions. Eradication of GV is the primary efficacy variable. Amsel criteria and Nugent scores will be determined to diagnose BV according to the definition in Section 3.3. See Section 3.3 for efficacy variable definitions. BV recurrence is the primary efficacy variable. Amsel criteria and Nugent scores will be determined at each follow-up visit to diagnose BV according to the definition in Section 3.3.1.

Safety Variables

Adverse Event

ICH E6 defines an AE as any untoward medical occurrence in a patient or clinical investigation participant administered a pharmaceutical product regardless of its causal relationship to the study treatment. An AE can therefore be any unfavorable and unintended sign (including an abnormal laboratory finding), symptom, or disease temporally associated with the use of medicinal product. AEs will be graded using the following general criteria:

- Mild: events require minimal or no treatment and do not interfere with the patient's daily activities.
- Moderate: events result in a low level of inconvenience or concern with the therapeutic measures. Moderate events may cause some interference with functioning.
- Severe: events interrupt a patient's usual daily activity and may require systemic drug therapy or other treatment. Severe events are usually incapacitating.

Serious Adverse Event

An adverse event or suspected adverse reaction is considered “serious” if, in the view of either the investigator or sponsor, it results in any of the following outcomes:

- Death,
- a life-threatening adverse event,
- inpatient hospitalization or prolongation of existing hospitalization,
- a persistent or significant incapacity or substantial disruption of the ability to conduct normal life functions, or
- a congenital anomaly/birth defect.
- Important medical events that may not result in death, be life-threatening, or require hospitalizations may be considered serious when, based upon appropriate medical judgment they may jeopardize the participant and may require medical or surgical intervention to prevent one of the outcomes listed in this definition.

5. SAMPLE SIZE CONSIDERATIONS

Sample size calculations were based on detecting a decrease in GV colonization rate from 80% among participants receiving placebo to as large as 44% among participants receiving amoxicillin. Using the two-sided Pearson Chi-Square test with Yates continuity correction, significance level of 0.05, and assuming an amoxicillin to placebo allocation ratio of 1:1, 82 women (41 in each arm) would provide 90% power to detect a difference in colonization rates of 36% (i.e. 44% colonization rate in the amoxicillin arm).

Assuming a 15% drop-out rate between enrollment and the TOC visit approximately 98 women will need to be randomized to obtain 82 women evaluable for the primary analysis. Assuming 40% of women without BV will have a positive NAAT test for GV at screening, approximately 245 women without BV will need to be screened to randomize 98 women in the study.

6. GENERAL STATISTICAL CONSIDERATIONS

6.1. General Principles

Tabulations will be used extensively to summarize the data. All continuous variables will be summarized using the following descriptive statistics: n (sample size), mean, standard deviation, median, maximum and minimum. The frequency and percentages (based on the sample size) of observed levels will be reported for all categorical measures. Wilson confidence intervals for binomial proportions and differences in binomial proportions will be computed for efficacy variables. Blaker confidence intervals for binomial proportions and differences in binomial proportions will be computed for safety variables. For the hypothesis tests comparing treatment groups with respect to safety outcomes, the two-sided Fisher's Exact test will be used. For the hypothesis tests comparing treatment groups with respect to efficacy outcomes, the two-sided Pearson Chi-Square test with Yates continuity correction will be used. For all tests, a 5% two-sided significance level will be used.

For all efficacy outcome measures, the Intention-to-Treat (ITT) population (see Section 6.3) will be used as the primary analysis population and the Per Protocol population will be used as a secondary analysis population. For all safety analyses, the Safety population will be used as the analysis population.

All summary tables will be structured with a column/sub-table for each treatment group (Amoxicillin, Placebo, and All Subjects). In general, all data will be listed by treatment group and/or subject, and when appropriate by visit number within subject. The total population size relevant to that table/column if applicable, including any missing observations will be displayed in the tables.

Note that in the data listings, Subject ID is the unique subject identifier, not the Study ID used on study and dates will not be included, only Study Day.

6.1.1. Pseudo Code

The following SAS® pseudo code will be used to calculate the following:

Chi-Square test at 5% two-sided significance level and odds ratio (and 95% asymptotic CI) from 2x2 table:

```
proc freq;
  Table treatment*analysis_variable / chisq;
  ods output ChiSq=outputdsn1;
  ods output RelativeRisks=outputdsn2;
run;
```

Note: Yates continuity correction is where Statistic = "Continuity Adj. Chi-Square";

Fisher's Exact test at 5% two-sided significance level:

```
proc freq;
  Table treatment*analysis_variable / exact;
  ods output FishersExact=outputdsn;
run;
```

95% Wilson CI for proportions/percentages:

```
proc freq;
  Table treatment*analysisvariable / binomial(wilson);
  ods output binomialcls=outputdsn;
run;
```

95% Wilson CI for difference in proportions (produces Newcombe CI):

```
proc freq;
  Table treatment*analysisvariable / riskdiff(cl=Wilson);
  Exact Riskdiff;
  ods output pdiffcls=outputdsn;
run;
```

95% Exact Blaker CI for proportions/percentages:

```
proc freq;
  Table treatment*analysisvariable / binomial(blaker);
  ods output binomialcls=outputdsn;
run;
```

6.2. Timing of Analyses

The final analysis will be performed after database lock when all subjects have been followed through Visit 2, the final study visit, at Day 15 (Window: Days 15-21).

6.3. Analysis Populations

6.3.1. Safety Analyses

All safety analyses will be performed in the Safety population. The Safety population includes all randomized subjects who received at least one dose of treatment. In the unlikely event of an error in randomization or treatment administration (i.e., incorrect product), subjects will be grouped by the product they actually received.

6.3.2. Efficacy Analyses

All efficacy analyses will be performed in the Intent-to-Treat (ITT) and Per Protocol (PP) analysis populations. The NAAT screening population will be used as the exploratory efficacy analysis population.

6.3.2.1. Intent-to-Treat (ITT) Population

The ITT population includes all randomized subjects, regardless of whether they received study treatment or were compliant with the administration procedures or schedule. In the unlikely event of an error in randomization or treatment administration (i.e., incorrect product), subjects will be grouped by their intended randomized assignment.

6.3.2.2. NAAT Screening Population

The NAAT Screening population includes all screened women who are evaluated for GV by NAAT.

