3.2.3 Exploratory Outcome Measures

 The demographic and behavioral factors among women in the NAAT screening population without vaginitis who are baseline GV positive and women who are baseline GV negative _____

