7.1 Visit 0 (Day -14 to -7) Screening

- Potential participants will be provided with a description of the study (purpose and study procedures) and asked to read and sign the Screening Informed Consent form, (SIC).
 The SIC form will be signed prior to performing any study eligibility procedures.
- Eligibility criteria will be reviewed with participants.
- Demographic information will be collected from the participant.
- Sexual history for the past 90 days will be collected.
- Medical history will be collected only on active conditions within one year prior to screening. All concomitant medications taken in the last 14 days prior to the screening visit will be recorded on the appropriate data collection form.
- A urine pregnancy test will be performed on all participants of childbearing potential and must be negative prior to administration of study product.
- A pelvic examination will be conducted for the collection of vaginal swab specimens for:

pH, whiff test, and wet prep microscopy (Amsel criteria with the exception of evaluation of vaginal discharge), Nugent score, NAAT for trichomonas, quantitative NAAT for GV, and future use. If the on-site microscopy reveals a vaginal infection (i.e., yeast, trichomonas, and BV/abnormal vaginal flora), the remaining specimens that were collected will be discarded as the participant is not eligible for the study. For this study, vulvovaginal candidiasis will be defined by the presence of budding yeast and/or pseudohyphae; trichomoniasis will be defined by the presence of motile trichomonads on wet prep or a positive NAAT for T. vaginalis; abnormal flora/BV by the presence of at least 2/3 of the following criteria − pH >4.5, positive whiff test, ≥ 20% clue cells. These stricter criteria will eliminate those women with intermediated flora as well as BV. We will not evaluate the presence of vaginal discharge per se due to the subjective nature of this observation. If these vaginal infections are found on the screening wet prep the participant will not be eligible for the study.

AFTER VISIT 0 ENDS AND PRIOR TO VISIT 1

 Women whose tests from the screening visit return positive for GV by NAAT, negative for abnormal flora/BV by Nugent score of 0-3 and negative for trichomonas by NAAT will return for the Enrollment visit, which is scheduled at the end of the screening visit.

- Women whose tests from the screening visit return negative for GV by NAAT will be called and informed that they are no longer eligible.

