- Women whose tests from the Screening visit return positive for GV by NAAT and also test positive for either BV or trichomonas will be called and informed that they are no longer eligible.

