11.4.1 Analysis Populations

Intent-to-Treat (ITT) Population: This analysis population includes all randomized participants.

The ITT population will be used as the primary efficacy analysis population.

Safety Population: This analysis population includes all randomized participants who received at least one dose of study treatment.

Per-Protocol (PP) Population: This analysis population includes all randomized participants who met all inclusion/exclusion criteria, are evaluable, adhered to the assigned study treatment regimen (as defined below), and returned to the study site for the ToC visit within the specified window (Visit 2 [Window: Day 15 -21]) and did not experience any of the following after enrollment:

- Unprotected vaginal sexual intercourse between Visit 1 and Visit 2
- New pregnancy reported by the subject
- Receipt of any antibiotic or intravaginal microbicide other than study drug

Participants are deemed evaluable if their BV and GV status can be determined at screening and their GV status can be determined at Visit 2. Participants who are missing Gram stain, GV NAAT, or Amsel results at screening are not evaluable. Participants who are missing GV NAAT results at the Visit 2 are not evaluable.

A Participant is considered adherent to the study treatment regimen if she uses at least 80% of the scheduled doses (i.e. at least 12 of the 14 doses) of study treatment, as assessed by the number of pills returned. If pill count cannot be assessed, participant report will be used to assess adherence.

In the unlikely event of an error in randomization or study product administration, participants will be grouped by the formulation they actually received in the PP and Safety analyses but will be grouped by their intended randomized assignment in the ITT analysis.

NAAT Screening Population: This analysis population includes all screened women who are evaluated for GV by NAAT.

The NAAT screening population will be used as the exploratory efficacy analysis population.

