3.2. Endpoints

Primary Endpoint:

- The proportion of participants with eradication of GV in each study arm at Visit 2 (Day 15-21) as assessed by nucleic acid amplification test (NAAT).

Secondary Endpoint:

- The proportion of participants reporting related adverse events (AEs) and serious adverse events (SAEs) in each study arm following the first dose of study product through Visit 2 (Day 15-21).

Exploratory Endpoint:

- The demographic and behavioral factors among women in the NAAT screening population without vaginitis who are baseline GV positive and women who are baseline GV negative.

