The exploratory outcome measure is the demographic and behavioral factors among women in the NAAT screening population without vaginitis who are baseline GV positive and women who are baseline GV negative. Gender, ethnicity, and race will be summarized by baseline GV status for subjects in the NAAT screening population in [Table 28](#). Age will be summarized by baseline GV status in [Table 29](#). Baseline GV status will be “Positive” or “Negative” as determined by NAAT at the screening visit.

Categorical and continuous sexual history questions will be summarized by baseline GV status ([Table 30](#), [Table 31](#)) and by treatment group at baseline and Visit 2 BV status, respectively ([Table 32](#), [Table 33](#), [Table 34](#), and [Table 35](#))

Additionally, the demographic and baseline characteristics of participants who were positive for BV by Nugent Score and Amsel Criteria and by treatment group at Visit 2 (Day 15-21) will be summarized. See [Table 36](#), [Table 37](#), [Table 38](#) and [Table 39](#).

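### The exploratory endpoint is limited to women without vaginitis, but the population named for Tables 28-31 is not, so women with laboratory-detected BV/abnormal flora or trichomonas could be counted

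*SAP*

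**What the plan says.** **Endpoint.** Protocol 3.2.3 describes the exploratory outcome among "women in the NAAT screening population without vaginitis who are baseline GV positive" and women who are GV negative. SAP 3.2 has the same restriction: "women in the NAAT screening population without vaginitis who are baseline GV positive and women who are baseline GV negative".

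**Population.** Protocol 11.4.1 defines the NAAT Screening population without it: "This analysis population includes all screened women who are evaluated for GV by NAAT". SAP 6.3.2.2 agrees: "The NAAT Screening population includes all screened women who are evaluated for GV by NAAT". SAP 6.3.2 names this as the exploratory efficacy analysis population.

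**Table instructions.** SAP 8.3 first restates the restricted outcome: "The exploratory outcome measure is the demographic and behavioral factors among women in the NAAT screening population without vaginitis who are baseline GV positive". The next sentence assigns Table 28 without the restriction: "Gender, ethnicity, and race will be summarized by baseline GV status for subjects in the NAAT screening population". The titles of Tables 28-31 name the NAAT Screening population. The N footnotes of Tables 28-30 refer to the GV NAAT population, and that of Table 31 to the NAAT Screening population, in each case by GV status only. No footnote or implementation note mentions vaginitis.

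**Screening flow.** Under Protocol 7.1, if on-site microscopy shows infection, "the remaining specimens that were collected will be discarded as the participant is not eligible for the study". The same section also provides for a second group: "Women whose tests from the Screening visit return positive for GV by NAAT and also test positive for either BV or trichomonas" are telephoned and told they are no longer eligible.

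**The concern.** The endpoint and the population that feeds its tables are different sets of women. The difference is made up of those who pass the bedside check, have a GV NAAT result, and then return an abnormal Nugent score or a positive trichomonas NAAT. They belong in the tables by the population definition and do not belong by the endpoint.

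Such women are unlikely to fall evenly across the two columns. Protocol 2.1 says GV is found in nearly all women with BV, whereas SAP 5 assumes 40% positivity in women without BV. Those with BV would therefore land mostly in the GV-positive column. Tables 30 and 31 compare recurrent BV, a BV diagnosis in the prior 6 months, the number of BV episodes in the prior 12 months, partners and condom use. A factor tied to BV could then appear as a difference by GV status among women described as free of vaginitis.

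The objective itself (SAP 3.1) carries no BV restriction, so the mismatch is with the stated endpoint. The primary and safety analyses do not use this population.

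**Working it through.** **1. Who can enter the tables**

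| Woman at screening | GV NAAT result? | In NAAT Screening population? | Meets endpoint restriction? |
|---|---|---|---|
| Yeast, trichomonads, or at least 2 of 3 bedside criteria | Normally no (specimens discarded, Protocol 7.1) | Normally no | No |
| Passes bedside check; Nugent 4-10 or trichomonas NAAT positive | Yes (Protocol 7.1 provides for this) | **Yes** | **No** |
| Passes bedside check; Nugent 0-3 and trichomonas NAAT negative | Yes | Yes | Yes |

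The second row is the gap. Inclusion criterion 2 (Protocol 5.1) confirms it can be filled: bedside findings come first, and trichomonas NAAT and Nugent score confirm later.

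**2. The plan's own figures**

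SAP 5 assumes 40% GV positivity in women without BV and 98 randomised: 98 / 0.40 = 245 screened. That leaves 245 - 98 = 147 GV negative. I take 98 and 147 as the restricted columns, treating the SAP's women without BV as women without vaginitis.

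**3. Size of the distortion (illustrative)**

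The documents do not give the share of affected women, their GV positivity, or any factor's prevalence. The following are assumptions:
- s = affected share of NAAT-tested women: 2%, 5%, 10%, 20%
- g = GV positivity in affected women: 95%, 70%, 40% (40% means no enrichment)
- factor prevalence 20% in women without vaginitis, whatever their GV status (true odds ratio 1.0), and p = 40% or 30% in affected women

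Formulas: A = 245 s / (1 - s). GV+ column = 98 + A g. GV- column = 147 + A (1 - g). Factor in GV+ = (98 x 0.20 + A g p) / (98 + A g), and likewise for GV-.

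Worked case, s = 5%, g = 0.95, p = 0.40:
- A = 245 x 0.05 / 0.95 = 12.9, of whom 12.25 are GV+ and 0.64 GV-
- affected share of the GV+ column = 12.25 / 110.25 = 11%
- factor in GV+ = (19.6 + 4.9) / 110.25 = 22.2%
- factor in GV- = (29.4 + 0.26) / 147.64 = 20.1%
- odds ratio = (0.222 / 0.778) / (0.201 / 0.799) = 1.14

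| s | A | Affected share of GV+ (g = 95%) | Factor, GV+ v GV- (g = 95%, p = 40%) | OR, g = 95%, p = 40% | OR, g = 70%, p = 40% | OR, g = 95%, p = 30% |
|---|---|---|---|---|---|---|
| 2% | 5 | 5% | 20.9% v 20.0% | 1.06 | 1.03 | 1.03 |
| 5% | 13 | 11% | 22.2% v 20.1% | 1.14 | 1.07 | 1.07 |
| 10% | 27 | 21% | 24.2% v 20.2% | 1.26 | 1.14 | 1.13 |
| 20% | 61 | 37% | 27.5% v 20.4% | 1.48 | 1.24 | 1.23 |

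At g = 40% the odds ratio is 1.00 throughout. The odds ratio is used here only to express the shift; Tables 28-31 do not report one.

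**The case against.** The strongest reply is that the SAP already states the restriction. The population definition is a parent set, the endpoint takes a subset of it, and SAP 8.3 repeats the restriction one sentence before the Table 28 instruction, so a careful programmer would apply it. That may happen, which is why these women could be counted rather than will be. But the instruction and all four shells use the unrestricted population, so two programmers could each follow the SAP and produce different denominators.

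Second, the number may be small. Protocol 7.1 expects its 2-of-3 bedside rule to remove intermediate flora as well as BV, and the schematic places GV testing after the no-vaginitis branch. This is fair and favours the lower shares in the table. It does not bring the number to zero, because the same section deals with women who are GV positive and later test positive for BV or trichomonas.

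Third, SAP 9.1 and 9.6 pair listings of enrolled women with listings of GV-negative women. If the GV-positive column were the enrolled women, it would contain no women with vaginitis. That pairing belongs to the listings; Tables 28-31 do not adopt it.

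Fourth, the shift is small against sampling error. With 98 v 147 women and 20% prevalence, the standard error of the log odds ratio is sqrt(1/19.6 + 1/78.4 + 1/29.4 + 1/117.6) = 0.33, so a null odds ratio has a 95% range of about 0.53 to 1.89, and even 1.48 lies inside it. This limits the practical harm but does not make the tables match their endpoint.

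Two smaller points stand. The endpoint wording leaves some doubt whether the restriction reaches the GV-negative women, and a rule is needed for a missing Nugent or trichomonas result.

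**Conclusion.** The concern holds. The documents give conflicting rules on who belongs in Tables 28-31, and following the population definition and shells would not report the endpoint as defined. That conclusion rests on the text alone.

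The size is uncertain. Under the stated assumptions the spurious odds ratio runs from 1.00 with no GV enrichment, through 1.03 to 1.14 at affected shares of 2% to 5%, up to 1.48 at a 20% share with 95% GV positivity and a factor twice as common in affected women. The direction, towards the GV-positive column, is supported by the documents for BV only; they give no GV rate for Nugent 4-6 or for trichomonas.

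The tables are descriptive, but they report the trial's only stated exploratory objective. They should be aligned before programming. The primary and safety analyses are unaffected.

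**What to change.** For Tables 28-31 only, restrict titles and denominators to women in the NAAT Screening population without vaginitis, in both GV columns. Use the documents' own criteria: no yeast or trichomonads on wet prep, fewer than 2 of the 3 bedside criteria (Protocol 7.1), Nugent 0-3, and a negative trichomonas NAAT. State this in the N footnotes, say how a missing Nugent or trichomonas result is handled, and report the number excluded by GV status, which will show how large the issue was. Leave the NAAT Screening population definition and all listings as they are.

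The cost is one flag derived from data already collected at screening, plus edited titles and footnotes in four tables. Under the assumed shares of 2%, 5%, 10% and 20%, about 5 of 250, 13 of 258, 27 of 272 or 61 of 306 women would leave these tables.
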